3.5.6 Other Assessments

Blinding Index: The BI will evaluate the success of blinding efforts incorporated in the study design.²⁷ When the subject completes all study assessments on Day 1, but prior to administering the Device Experience Questionnaire, the subject and the physician investigator will be asked to indicate which treatment allocation they believe the subject received. If the respondent selects "I don't know", then the second question asks the respondent to provide a best guess, with a binary outcome: real medication or placebo. The final question asks the respondent to indicate the reason(s) why they chose their response to question 1 and question 2 (if applicable). The reason(s) will be captured as open-ended commentary by the respondent. A sample BI questionnaire is provided in Appendix 8.1.

Device Experience Questionnaire-Subject: The Device Experience Questionnaire-Subject will evaluate the subject's experience with the device during the study. Each subject will be asked to rate their agreement (Strongly Disagree, Disagree, Neutral, Agree, or Strongly Agree) to

Confidential

4 questions about using the device. Additional comments related to each question will be documented in the questionnaire. Question 5 allows the subjects to provide other comments about the device that were not captured by the previous 4 questions. The questionnaire will be administered when the subject completes all study assessments on Day 1, including the BI, prior to leaving the study centre.

Device Experience Questionnaire-Study Staff Administering Treatment: The Device Experience Questionnaire-Study Staff Administering Treatment will evaluate the study staff's experience with the device during the study. Each study staff administering treatment will be asked to rate their agreement (Strongly Disagree, Disagree, Neutral, Agree, or Strongly Agree) to 6 questions about using the device. Additional comments related to each question will be documented in the questionnaire. Question 7 allows the study staff to provide other comments about the device that were not captured by the previous 6 questions. Each study staff who administered treatment to subjects will complete one questionnaire for the study, which will be administered after all subjects to be treated by study staff have completed all Day 1 assessments.

3.5.7 Appropriateness of Measurements

The most recent version of the CONSORT statement on guidelines for parallel group randomised trials indicates that information on "how the success of blinding (masking) was assessed" is no longer recommended because of a lack of empirical evidence supporting the practice as well as theoretical concerns about the validity of any such assessment.²⁸ Conceptually, investigators are able to assess the success of blinding by asking participants and others (eg, outcome assessors) which treatment they believe was allocated. In theory, if blinding was successful, these people should not be able to guess the treatment more frequently than that expected by chance. Tests of the success of blinding hinge on that theoretical model. In reality, however, blinding could be successful, but people involved in the trial might deduce the treatment through supplementary information. Differential levels of side-effects or harms could yield strong clues, as can therapeutic benefits, or other pharmacologic/pharmacodynamics properties of the treatment. Nevertheless, a blinding assessment (ie, BI) to explore the integrity of the study design and masking of treatment will be performed when the subject completes all assessments on Day 1. The BI will be performed separately by the physician investigator and subject. Analysis methods proposed by Bang and collegues,²⁷ which have been mostly described through simulations rather than application in clinical trials, will be used.

All other assessments to be used in this study are commonly used, standard measurements in AOM studies. Assessment of device experience is common in studies of drug-device combination products.

4 ADVERSE EVENT REPORTING

Throughout the course of the study, all AEs will be monitored and recorded on an AE eCRF, including the AE's description, start and end date, seriousness, severity, action taken, and relationship to the study drug. If AEs occur, the first concern will be the safety of the subjects. All AEs will be followed until resolved or stable and the outcome documented on the eCRF.

4.1 Definitions and Criteria

4.1.1 Adverse Events

Per ICH E2A²⁹: An AE is any untoward medical occurrence in a patient or clinical investigation subject administered a pharmaceutical product and which does not necessarily have to have a causal relationship with this treatment. An AE can therefore be any unfavorable and unintended sign (including an abnormal laboratory finding, for example), symptom, or disease temporally associated with the use of a medicinal product, whether or not considered related to the medicinal product.

Medical interventions such as surgeries, diagnostic procedures, and therapeutic procedures are not AEs but the action taken to treat the medical condition. They should be recorded as treatment of the AEs.

Any AE that has an onset on or after the dose of study drug, or any pre-existing condition that has worsened on or after the first dose of study drug will be considered a treatment-emergent adverse event (TEAE).

4.1.2 Serious Adverse Events

An SAE or reaction is any untoward medical occurrence that at any dose:

- Results in death
- Is life-threatening
- Requires inpatient hospitalisation or prolongation of existing hospitalisation
- Results in persistent or significant disability or incapacity
- Is a congenital anomaly or birth defect
- Is an important medical event (eg, intensive treatment in an emergency room or at home for allergic bronchospasm; blood dyscrasias or convulsions that do not result in hospitalisation; development of drug dependency or drug abuse; or malignancy tumors [histologically different from primary tumor])

Note: The term "life-threatening" in the definition of "serious" refers to an event in which the subject was at risk of death at the time of the event; it does not refer to an event that hypothetically might have caused death if it were more severe.

Medical and scientific judgment should be exercised in deciding whether expedited reporting is appropriate in other situations, such as important medical events that may not be immediately life-threatening or result in death or hospitalisation, but may jeopardise the subject or may require intervention to prevent one of the other outcomes listed in the definition above. These events should also usually be considered serious.

Examples of such events are intensive treatment in an emergency room or at home for allergic bronchospasm; blood dyscrasias or convulsions that do not result in hospitalisation; or development of drug dependency or drug abuse.

Seriousness (not severity) serves as a guide for defining regulatory reporting obligations. An SAE is not necessarily severe; eg, an overnight hospitalisation for a diagnostic procedure must

be reported as an SAE even though the occurrence is not medically serious. By the same token, a severe AE is not necessarily serious: nausea lasting several hours may be rated as severe but may not be considered serious.

4.1.3 Unexpected Adverse Drug Reactions

An unexpected adverse drug reaction (ADR) is a reaction for which the nature or severity is not consistent with the applicable product information (IB). Until product information is amended, expedited reporting is required for additional occurrences of the reaction. Reports that add significant information on specificity or severity of a known, already documented SAE constitute unexpected events. For example, an event more specific or more severe than described in the IB would be considered "unexpected." Specific examples would be (a) acute renal failure as a labeled ADR with a subsequent new report of interstitial nephritis and (b) hepatitis with a first report of fulminant hepatitis.

Guidance on reporting AEs and SAEs is described in Section 4.2.

4.1.4 Assessing Intensity and Relationship

All AEs will be assessed on 2 descriptive parameters: intensity and relationship to the study drug:

- Intensity refers to the severity of an event and references impact on a subject's functioning.
- Relationship refers to the likelihood that the event being assessed was caused by the study drug.

Intensity

Each AE will be classified according to the following criteria:

Mild:	The AE does not interfere in a significant manner with the subject's normal level of functioning.
Moderate:	The AE produces some impairment of functioning, but is not hazardous to the subject's health.
Severe:	The AE produces significant impairment of functioning or incapacitation and is a definite hazard to the subject's health.

When changes in the intensity of an AE occur more frequently than once a day, the maximum intensity for the experience should be noted. If the intensity category changes over a number of days, those changes should be recorded separately (with distinct onset dates).

Relationship

The investigator must assess the causality of an AE (including SAEs) to the use of a study drug using a 2-category scale (not related or related) based on clinical judgment and using all available information, and may include consideration of the following factors:

- Possible alternative causes of the AE, including the disease under treatment, pre-existing conditions, concomitant use of other drugs, and presence of environmental or genetic factors
- The temporal association between study drug exposure and onset of the AE
- Whether the manifestations of the AE are consistent with known actions or toxicity of the study drug
- Whether the AE resolved or improved with stopping use of the study drug; judgment should be used if multiple products are discontinued at the same time
- Positive rechallenge
- Positive dechallenge (resolution upon stopping suspect study drug, in absence of other intervention or treatment)

The causal relationship between the study drug and the AE will be assessed using one of the following categories shown in Table 4.1:

Table 4.1: Adverse Event Causality

Category	Definition
Not Related	An AE is not associated with study medication if no causal relationship exists between the study drug and the AE, but an obvious alternative cause exists, eg, the subject's underlying medical condition or concomitant therapy.
Related	An AE is attributed to the study medication if there is reasonable/plausible possibility that the AE may have been caused by the study drug:

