11. SAFETY PARAMETERS

Safety parameters will be listed for the Randomized Population and summarized for the Safety Population unless otherwise noted.

11.1 **AEs**

AEs reported from time of first dose through EOS will be coded according to MedDRA® version 21.1 or later. Each reported AE will be mapped to a PT and SOC. Aside from parameters collected on the eCRF, listings will include date and time of study treatment dosing, MedDRA PT and SOC, Study Day, whether or not the AE is ongoing, AE duration, and whether or not the AE resulted in study discontinuation. For AEs that are ongoing, AE end date will be imputed with subject-level EOS date for the duration calculation.

A treatment-emergent AE (TEAE) will be defined as an AE that began or worsened during or after study treatment dosing on Day 1 and no later than on Day 2. AEs with insufficient date or time information to determine whether or not they were treatment-emergent will be considered treatment-emergent. AEs that began or worsened in severity from Day 3 through EOS will be defined as non-treatment-emergent. AEs that began or worsened in severity before first dose will be recorded as medical history.

All TEAEs will be listed. In addition, separate listings will be done for:

- Treatment-emergent SAEs (TESAEs), to include seriousness criteria
- TEAEs that resulted in study treatment interruption or dose reduction

Confidential Page 16 of 33

- TEAEs that results in discontinuation from the study or study treatment (excluding deaths)
- TEAEs that resulted in death
- Non-treatment-emergent AEs

Listings will be done for the Safety Population.

Incidence of all TEAEs will be summarized by SOC and PTs within SOCs, sorted alphabetically by SOC and PT within SOC unless otherwise noted. In addition, separate summaries will be done for:

- TEAEs assessed as related to study treatment
- TEAEs by maximum severity, with both SOCs and PTs within SOCs sorted by descending incidence among all Study Participants combined
- TESAEs
- TESAEs assessed as related to study treatment

In summaries by relationship to study treatment and maximum severity, missing relationship will be considered related and missing severity will be considered severe. Only the most related TEAE per subject for a given PT will be counted in summaries by relationship; similarly, only the most severe TEAE will be counted in summaries by severity.

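### Protocol 4.1.4 adds a health-hazard condition to two of its three AE intensity grades, so the scale is not exhaustive and the SAP's severity summaries could understate severe events

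*Protocol*

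**What the plan says.** Protocol 4.1.4 opens with a definition on one dimension: "Intensity refers to the severity of an event and references impact on a subject's functioning". Every AE must then be placed in one of three grades:

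- Mild turns on functioning alone: interference must fall short of significant, and hazard is not mentioned.
- Moderate combines a degree of impairment with a second condition, that no hazard to health is present.
- Severe reverses that second condition and joins it to a larger impairment: "The AE produces significant impairment of functioning or incapacitation and is a definite hazard to the subject's health".

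Protocol 4.1.2 keeps severity apart from seriousness. It says "Seriousness (not severity) serves as a guide for defining regulatory reporting obligations", and it gives an example: "a severe AE is not necessarily serious: nausea lasting several hours may be rated as severe but may not be considered serious".

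The SAP has no intensity scale, so 4.1.4 is the only one. SAP 4.2.1 includes severity in the first primary endpoint, and SAP 15 logs this as a change from the protocol, whose endpoint wording refers only to AEs recorded. SAP 11.1 plans a table of TEAEs by maximum severity and separate lines for severe and moderate TEAEs in the overall summary. In the summaries by relationship and maximum severity, "missing relationship will be considered related and missing severity will be considered severe". Protocol 5.2.7.2 also summarises moderate AEs, severe AEs and TEAEs by maximum severity.

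**The concern.** The definition uses one axis and the grades use two. Severe needs a large functional impact and a definite hazard together; Moderate needs a lesser impact and no hazard. An investigator faced with a disabling event that does not endanger the subject, such as prolonged nausea or a very troublesome headache, has no grade that plainly fits. The nearest one that does not assert a hazard is Moderate.

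Safety is the primary objective, and Protocol 1.5 reports no earlier clinical study of OP0201 in humans. The propellant-placebo events that Protocol 1.5 cites (nasal discomfort, epistaxis, headache) include complaints for which functional impact is the natural grading dimension. If such events are steered away from the top grade by the hazard condition, the severe-TEAE line no longer reports what the definition of intensity says it should.

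**Working it through.** The plan states no figure to reproduce. The check is whether the three definitions cover every case.

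**Inputs.** From Protocol 4.1.4: three levels of impairment (not significant; some; significant or incapacitating) and two of hazard (absent; present), so 3 × 2 = 6 combinations. From Protocol 5.2.1: 12 subjects per arm, about 24 in all.

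**Enumeration.** The literal reading treats some and significant as successive steps. The broad reading lets some impairment include significant impairment.

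| Impairment | Hazard | Literal | Broad |
|---|---|---|---|
| Not significant | No | Mild | Mild |
| Not significant | Yes | Mild | Mild |
| Some | No | Moderate | Moderate |
| Some | Yes | none | none |
| Significant or incapacitating | No | none | Moderate |
| Significant or incapacitating | Yes | Severe | Severe |

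On the literal reading 2 of 6 combinations have no grade. On the broad reading 1 of 6 has none, and an incapacitating event without a hazard is graded down, against the section's own definition. One could argue the remaining combination (some impairment, with hazard) into Mild, because the interference is not significant; a hazardous event would then take the lowest grade.

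**Against 4.1.2.** The protocol's example allows several hours of nausea to be rated severe. Under 4.1.4 that rating is open only if the investigator also judges the nausea a definite hazard to health. The example says nothing of a hazard.

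**Weight of one subject.** Incidence counts subjects, and SAP 11.1 keeps only the most severe TEAE. One subject moved between Moderate and Severe changes the arm's severe-TEAE incidence by 1/12 = 8.3 percentage points, or 1/24 = 4.2 points over both arms. The change is zero if that subject already has another severe TEAE.

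**How often.** The documents give no rate for such events. If a proportion p of subjects had one (an assumption), the chance of at least one is 1 − (1 − p)^n:

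| Assumed p | n = 12 | n = 24 |
|---|---|---|
| 1% | 11% | 21% |
| 5% | 46% | 71% |
| 10% | 72% | 92% |

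For scale, Protocol 1.5 gives nasal discomfort 4.8% and headache 1.6% of any grade on propellant placebo in trials of 2 to 6 weeks. Added together, 12 × 6.4% = about 0.8 per arm. Only a part of these would be disabling, after a single dose, so the lower end of the range is the more plausible.

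**The case against.** The strongest reply is that this is a small wording matter. Some impairment has no stated upper limit, so an incapacitating event can be called Moderate. The threshold for a definite hazard is undefined, so an investigator may judge hours of nausea to meet it. Both arms use the same scale under blinding, SAP 11.1 names no test for severity, no success criterion depends on it, and every TEAE is listed. In about 24 subjects a disabling event would be seen whatever its grade.

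Much of that stands, and it limits the size of the point. It does not make the grades exhaustive: the broad reading buys coverage by grading incapacity as Moderate.

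A reader might infer more than the documents support:

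- *That Severe all but duplicates Serious.* Protocol 4.1.2 defines seriousness by a list of outcomes and important medical events, and separates it from severity in both directions. A definite hazard need not meet any of those criteria.
- *That the nausea example flatly contradicts the scale.* It says only that such nausea may be rated severe, so the criteria conflict without one negating the other.
- *That sites will leave ungradable events blank and have them counted as severe.* Protocol 4.1.4 requires a grade for every AE, and Protocol 5.1 provides queries for omissions. The missing-severity rule covers only what stays missing after that.
- *That every reclassified event moves incidence by 8.3 points.* The figure is per subject, and a maximum.
- *That 2 of 6 is a frequency.* It counts combinations, not events.
- *That dizziness is a known effect of the spray.* It is not among the propellant events in Protocol 1.5. Protocol 3.5.4 lists it as an AOM symptom, and under Protocol 4.2.1 a symptom present before dosing is an AE only if it worsens.

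**Conclusion.** The point holds as a defect in the grading scale. Protocol 4.1.4 defines intensity by functional impact and then makes two grades depend on hazard. A significantly impairing AE that is not a definite hazard is ungradable or graded down, and some impairment with a hazard has no clear grade. Because the SAP makes severity part of its first primary endpoint and relies on this scale, the moderate, severe and maximum-severity summaries could understate severe events.

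The size is modest: up to 8.3 percentage points in an arm for each reclassified subject, in summaries that are descriptive. TEAE incidence, SAEs and relatedness do not change. The conclusion assumes that investigators apply the written definitions. It does not show that a finding of no severe TEAEs would be produced by the scale, because the documents give no rate for the events concerned. The place in a primary endpoint rests on the SAP; the protocol brings severity in only through its analysis section. The matter should be put right but does not threaten the trial's main safety counts.

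**What to change.** Reconcile Protocol 4.1.4 with its own opening definition and with 4.1.2, so that the three grades are exhaustive and rest on functional impact. One way is to remove the hazard clause from Moderate and from Severe and repeat the revised wording in the eCRF guidance. Events that may jeopardise the subject are then captured by the seriousness criteria in 4.1.2, which already provide for them. Other wordings would also close the gap; the choice is the sponsor's.

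The text change is two clauses and a line of guidance, but that is not the whole cost. SAP 9.2 describes all subjects as enrolled under the existing protocol, so any AE already recorded would need its grade checked by the investigator, under blind, before database lock, and the SAP should say that this was done. Slightly more AEs may be graded severe as a result.

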5.2.7.2 Adverse Events

AEs will be coded in accordance with the latest version of the Medical Dictionary for Regulatory Activities (MedDRA). Incidence for all reported AEs will be summarised overall (regardless of severity or relationship to study drug), moderate AEs, and severe AEs. Additionally, a summary

of SAEs and AEs leading to early termination from the study will be presented along with corresponding data listings.

The incidence of TEAEs will be summarised as the number and percentage of subjects and events reported by treatment and overall for each System Organ Class and Preferred Term using the Safety Analysis Population. TEAEs will also be summarised by maximum severity and relationship to study drug.

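### AE records split at each between-day intensity change are never rejoined, so part of one Day 1 reaction can be reported as non-treatment-emergent and a late peak can leave the TEAE severity summaries

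*Protocol*

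**What the plan says.** Protocol 4.1.4 has two recording rules. Where intensity changes more often than once a day, "the maximum intensity for the experience should be noted". Where it changes across days, the rule is different: "If the intensity category changes over a number of days, those changes should be recorded separately (with distinct onset dates". No direction is given, so a fall from moderate to mild is covered as well as a rise.

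On counting, Protocol 5.2.7.2 states: "The incidence of TEAEs will be summarised as the number and percentage of subjects and events reported by treatment and overall". The SAP speaks of incidence and specifies no event count. Its Section 15, which lists changes from the protocol, does not say that event counts were dropped.

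On classification, SAP 11.1 defines a TEAE as "an AE that began or worsened during or after study treatment dosing on Day 1 and no later than on Day 2". It continues: "AEs that began or worsened in severity from Day 3 through EOS will be defined as non-treatment-emergent". The latter have their own table (14.3.1.4) and listing (16.2.7.2). Protocol 4.1.1 defines TEAEs with no upper day limit, and Section 15 does not list the Day 2 limit as a change.

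SAP 11.1 has two collapsing rules, both among TEAEs only: "Only the most related TEAE per subject for a given PT will be counted in summaries by relationship" and "similarly, only the most severe TEAE will be counted in summaries by severity". AE duration is a listing field.

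**The concern.** The recording rule produces several dated records for one reaction, and the classification rule acts on dates. Nothing in either document rebuilds the event before it is classified. Followed as written, the two rules can put the later part of a reaction that began within minutes of dosing into a table meant for events unconnected in time with dosing.

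The more serious case is late worsening. The SAP's own wording sends a worsening from Day 3 onward to the non-treatment-emergent set. The peak of a Day 1 reaction then disappears from the TEAE summary by maximum severity (Table 14.3.1.2.3) and from the severe-TEAE line of the overall summary (Table 14.3.1.1). The rule that keeps the most severe TEAE cannot recover it, because it looks only among TEAEs. Safety is the primary objective, and AE severity is part of the primary endpoint in SAP 4.2.1.

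**Working it through.** The plan gives no figure to reproduce. The check applies the two rules to assumed courses.

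Inputs:
- New record at each between-day change of category: Protocol 4.1.4.
- Record dated Day 1-2 is a TEAE; record dated Day 3 or later is not: SAP 11.1, taking the record's onset date as the date it began.
- Duration = end date minus start date plus 1: SAP 8.6.
- 12 subjects per arm: Protocol 5.2.1.
- Assumption, not in the documents: the six courses below, all starting on Day 1 after dosing.

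Records = 1 + number of between-day category changes.

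| Course | Records | TEAE | Non-TEAE | Highest TEAE severity | True highest |
|---|---|---|---|---|---|
| A: mild D1, moderate D2, mild D3 | 3 | 2 | 1 | moderate | moderate |
| B: severe D1-2, moderate D3-4, mild D5-6 | 3 | 1 | 2 | severe | severe |
| C: mild D1-2, severe D3-4, mild D5 | 3 | 1 | 2 | mild | severe |
| D: moderate D1, mild D2, resolved D3 | 2 | 2 | 0 | moderate | moderate |
| E: mild/moderate alternating daily, D1-7 | 7 | 2 | 5 | moderate | moderate |
| F: mild throughout D1-5 | 1 | 1 | 0 | mild | mild |

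Reading the table:
- **Non-TEAE table.** In A, B, C and E the same subject is in both the TEAE and the non-TEAE tables. One such subject adds 1/12 = 8.3 percentage points to that arm in Table 14.3.1.4. In D and F nothing is misplaced, because no category change falls on Day 3 or later.
- **Severity.** Only C loses its peak: it is reported as a mild TEAE although the reaction became severe. This case does not depend on how an onset date is read, since worsening from Day 3 is named in the SAP definition.
- **Event count.** Each course is one event. With the SAP's Day 2 limit, the TEAE record count is 1 or 2. With the protocol's open-ended definition and each record's onset date taken as an onset, it is 1 to 7.
- **Subject count.** Each course gives 1 subject with a TEAE, 1/12 = 8.3%, with or without splitting.
- **Duration.** A reaction that is moderate on Days 1-2 and mild on Days 3-6 is listed as 2 - 1 + 1 = 2 days and 6 - 3 + 1 = 4 days, not as 6 - 1 + 1 = 6 days.

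After collapsing to one record per reaction (first onset, highest intensity), every course gives 1 event, 1 TEAE, 0 non-TEAE records and 1 subject, and C is reported as severe.

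**The case against.** The strongest reply is that the text does not force these results. Protocol 4.1.4 speaks of recording changes in an AE separately; it does not call each change a new AE. The eCRF and the data management plan are not among the documents, so a link between records may exist. An improving reaction began on Day 1 and did not worsen, so by a careful reading it is not a non-treatment-emergent AE at all. The SAP, which prevails over the protocol on analyses, specifies no event-count table and no duration summary, and it already collapses TEAEs in its relationship and severity summaries. With about 24 subjects, abutting rows of one Preferred Term would be visible in a listing. The effect needs the SAP's Day 2 limit; under Protocol 4.1.1 alone, the later records would stay treatment-emergent.

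Most of this stands, and it limits the point. A reader might infer that TEAE incidence is inflated, that every improving tail is certain to be reported as non-treatment-emergent, or that one arm is favoured. The documents support none of these. Subject-level incidence is unchanged, the improving case depends on one reading of the onset date, and nothing indicates how often intensity will change across days or in which arm.

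The reply does not answer late worsening, where the SAP text itself moves the peak out of the TEAE set. Nor does it supply the missing rule: an improving record carries a mandated onset date and has no stated class, so a programmer working from dates would place it by that date.

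**Conclusion.** The point holds as a conflict between two stated rules with no rule to join them. A Day 1 reaction that changes category on Day 3 or later can be reported in part as a separate non-treatment-emergent AE. If the change is a worsening, its peak is lost from the TEAE severity summaries. Any event count kept under Protocol 5.2.7.2 is inflated, and listed durations are cut into segments.

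The size is 0 to 5 misplaced records per reaction in the assumed courses, and 8.3 percentage points of an arm in Table 14.3.1.4 for each affected subject. The number of affected subjects cannot be estimated from the documents. The result assumes that records reach the analysis unlinked and, for improving records only, that the onset date is read as the date the AE began. The number and percentage of subjects with a TEAE starting on Days 1-2 are not affected. The change should be made, but it does not threaten the main TEAE incidence result.

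**What to change.** In SAP 11.1, before any counting, collapse contiguous records of the same subject and Preferred Term into one event:
- onset = first start, and end = last end;
- severity = maximum over all segments;
- emergence set by the first onset or, for a pre-existing condition, by the first worsening.

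Add that a record showing only improvement is never a new or a non-treatment-emergent AE. Define contiguous, for example as a record starting on the day the previous one ends or the day after. State whether the event counts of Protocol 5.2.7.2 are kept, and enter the answer in SAP Section 15. Reconcile the SAP's Day 2 limit with the open-ended definition in Protocol 4.1.1, and list any difference in Section 15.

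The cost is a little programming and a check at coding that the records of one event carry the same Preferred Term. Two distinct reactions with the same term and abutting dates would be merged, so merged records should be reviewed before unblinding. No eCRF change is needed. That matters because SAP 9.2 describes enrolment in the past tense, so a new link field might come too late.
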